16.1 MRI

Descriptive statistics for the number of T1 Gd+ lesions, new/enlarging T2 lesions and T2 volume at each visit (early treatment discontinuers during OLE will be presented at 'EOT' visit) during the OLE will be provided by treatment group and overall on the mITT-OLE analysis set.

Mean number of T1 Gd+ lesions and new/enlarging T2 lesions will be presented as a by-visit line plot for each treatment group during the OLE on the mITT-OLE analysis set, with a vertical line segment at each visit representing ± standard error (SE) (jittered if needed for legibility), and with all treatment groups included in a single figure.

A listing will be provided for the MRI assessment data, by participant and by timepoint for the OLE treatment period.

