M2951 (25 mg tablets) will be administered orally daily for 48 weeks as needed based on the dose (e.g., 3×25 mg tablets for a 75 mg dose). Dosing will be either 25 mg once daily, 75 mg once daily, or 75 mg twice daily. Matched placebo tablets will be provided. For participants who choose to enroll in the OLE, M2951 may be administered for a total of up to 432 weeks.

Reference therapy: dose/mode of administration/dosing schedule: Tecfidera (120 or 240 mg hard capsules) will be used as an active control. For the first 7 days, Tecfidera is administered orally at 120 mg twice daily. Following this and for the duration of treatment, Tecfidera is administered orally at 240 mg twice daily orally. Detailed recommendations for the use of this product are described in the summary of product characteristics or prescribing information.

Planned trial and treatment duration per participant: Total duration of participation is approximately 440 to 448 weeks for participants who choose to participate in the optional OLE Period and approximately 392 days (56 weeks) for participants who do not participate in the optional OLE Period. Total duration includes:

- Screening: 28 days (4 weeks);
- Treatment: 168 days (24 weeks);
- Blinded treatment extension: 168 days (24 weeks);
- Tecfidera Washout for participants who were in Tecfidera arm: 4 to 8 weeks;
- Optional OLE Period (up to 384 weeks);
- 4-week Safety Follow-Up/End of Trial Visit: 28 days (4 weeks).

After completing the 48-week main study, participants will be offered the opportunity to participate in an optional OLE Period with M2951 up to 384 weeks.

Once the long-term follow-up study is open for enrollment in their country (i.e., once the Sponsor, upon agreement with Health Authorities/Ethics Committees, will have notified sites), participants in the OLE Period will have the option to transition into the long-term follow-up study under a new protocol for continued treatment. Upon Sponsor site notification, all participants will be asked to return for an OLE End of Treatment Visit within 30 days.

- For participants entering the long-term follow-up study under a new protocol, their OLE End of Treatment Visit in the current study is also their first visit in the long-term follow-up study. Therefore, these participants are neither required to enter the 4-week Safety Follow-up Period nor to undergo a 4-week Safety Follow-up Visit/End of Trial Visit.

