[figure not shown]

Figure 2 Trial Design – Optional OLE Period

BID=twice a day; D=Day; IMP= investigational medicinal product; MRI=magnetic resonance imaging; OLE=Open-label Extension; QD=once a day.

- a Participants who entered the OLE Period initially received M2951 at 75 mg once daily. After review of the efficacy and safety data from the primary analysis at 24 weeks and the blinded extension analysis at 48 weeks, the optimal tested dose is 75 mg twice daily. Accordingly, once IMP for this dose is available at the study site, participants participating in the OLE Period will either enter the OLE Period on the 75 mg twice daily dose or will be switched to the 75 mg twice daily dose.
 - For participants entering the OLE after receiving M2951 during the 48-week main study, the Week 48 Visit is considered the Day 1 Visit for the OLE period.
- b For participants entering from Tecfidera treatment arm, treatment with M2951 will only commence if a participant who received Tecfidera during the 48-week main study has an absolute lymphocyte count ≥ 800/mm³ following 4 weeks of washout. If the participant does not have an absolute lymphocyte count ≥ 800/mm³ following 8 weeks of washout, he or she will be discontinued from the study.
- c Denotes efficacy visits only. Safety visits will be conducted every 2 weeks during the first 16 weeks of treatment, then monthly during the OLE period until Week 96, then 3-monthly until Week 192, then 6-monthly until Week 384.
- d An interim analysis will be performed at Week 60 of the OLE period. A further interim analysis will be planned at the appropriate time point considering the visits schedule around the time of the trigger for the primary analysis of the Phase III RMS studies.
- e Between Week 96 and Week 384 regular Telephone Visits will occur. See Table 3 for the schedule and Section 7.1.6.1 for details of the Telephone Visits.

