7.3.1 Brain Magnetic Resonance Imaging Scans

MRI scans will be performed at Screening, at 4-week intervals from Week 12 to 24, and at the End of Treatment Visit at Week 48 (including for participants receiving Tecfidera who choose to enter

the OLE Period). For participants in the OLE Period, an MRI will also be performed at Day 1 (except for participants who received Tecfidera during the 48-week parent study and had an MRI at the End of Treatment Visit at Week 48), Week 48, and then every 48 weeks up to and including the OLE End of Treatment Visit. If a participant discontinues the study more than 4 weeks after his or her most recent MRI, an MRI may be obtained at the 4-week Safety Follow-up Visit. The Screening MRI scan should be acquired before randomization and dosing to allow for the readouts to be read by the central MRI reader (approximately 7 days).

Gadolinium will be used to enhance T1-weighted lesions and to optimize clarity and accuracy of reporting. As gadolinium is excreted renally, participants with acute renal insufficiency (eGFR < 45 mL/min/1.73 m²) will be excluded from the trial (see Section 5.3.2, exclusion criterion 33).

Brain MRI scans will be performed according to a standardized imaging protocol before and after the administration of single-dose gadolinium.

Images will be assessed and reported by an independent, blinded, centralized MRI reading service, provided by PPD.

The assessment will be performed in the absence of clinical information. Further details, including the scans required and the optimal MRI workflow, will be provided in a separate Imaging Manual that will be provided to each trial site by PPD.

All MRI images will be reviewed and reported locally by a radiologist for safety. The local report will contain only nonMS pathology and will be provided to the Treating Investigator.

Note: Where possible, the use of high dose corticosteroids should be avoided in the 3-week period prior to a scheduled MRI scan. In participants receiving corticosteroids for an MS relapse, there must be a 3-week interval between the last dose of corticosteroids and the scheduled MRI scan.

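### SAP 16.1 reports new/enlarging T2 lesions in the OLE as raw counts per visit, although the time each count covers differs by design

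*SAP*

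**What the plan says.** SAP 16.1 plans two summaries of new/enlarging T2 lesions on the mITT-OLE set. The first is a table: "Descriptive statistics for the number of T1 Gd+ lesions, new/enlarging T2 lesions and T2 volume at each visit", with early discontinuers shown at an EOT visit. The second is a figure: "Mean number of T1 Gd+ lesions and new/enlarging T2 lesions will be presented as a by-visit line plot for each treatment group". Neither sentence gives a denominator, a scan interval or a reference scan. Gd+ T1 and T2 counts are handled identically.

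The scan schedule is in Protocol 7.3.1. After Screening, main-study scans are taken "at 4-week intervals from Week 12 to 24, and at the End of Treatment Visit at Week 48". For participants entering from M2951, Figure 2 of Protocol 5.1 notes that "the Week 48 Visit is considered the Day 1 Visit for the OLE period". In the OLE, scans follow at "Week 48, and then every 48 weeks up to and including the OLE End of Treatment Visit". An OLE Day 1 scan is required "except for participants who received Tecfidera during the 48-week parent study and had an MRI at the End of Treatment Visit at Week 48". The Synopsis lists "Tecfidera Washout for participants who were in Tecfidera arm: 4 to 8 weeks", and Protocol 5.5.1 allows up to 1 further week to schedule OLE Day 1.

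SAP Appendix 3 lists OLE Week 0 as an MRI analysis visit. Its window takes scans from main-study day 189 to before OLE day 30, so it holds the main-study Week 48 scan.

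**The concern.** A count that accrues between two scans grows with the gap between them, even when disease activity is unchanged. The scheduled gaps are 24 weeks before OLE Week 0 and 48 weeks at later OLE visits. They are longer for former Tecfidera participants at OLE Week 48 and variable at EOT. In a raw mean by visit, a change in scan spacing cannot be told apart from a change in lesion formation. Part of the former-Tecfidera interval is also time off study drug.

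The OLE objective includes long-term efficacy, and a line plot invites a reading of trend. The plan scales comparable counts elsewhere. SAP 16.2 divides qualified relapses by follow-up on treatment. Protocol 8.5.3 analyses main-study T2 counts with a negative binomial model like the primary one, whose offset (Protocol 8.5.2) is the log number of scans. Only the OLE T2 counts have no adjustment for opportunity.

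**Working it through.** The documents state no figure on this point, so there is nothing to reproduce. The check is schedule arithmetic.

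**Inputs**
- Scans at main-study Weeks 24 and 48, then every 48 weeks in the OLE (Protocol 7.3.1).
- Main-study Week 48 is OLE Day 1 for entrants from M2951 (Protocol 5.1, Figure 2). The gap closing at OLE Week 0 is therefore 48 − 24 = 24 weeks.
- Former Tecfidera participants keep the Week 48 scan and add a washout of 4 to 8 weeks, plus up to 1 week for scheduling. Their gap at OLE Week 48 is 48 + 4 = 52 to 48 + 9 = 57 weeks, which is 8% to 19% longer than 48.
- The Screening scan falls s = 0 to 4 weeks before Day 1 (Protocol Table 1).
- Assumption: the reference scan is not defined in either document, so all three candidates are worked through.

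**Formula.** With a constant rate r per year, expected count = r × (weeks since reference scan) / 52.18. The printed ratio of two visits is then the ratio of their intervals.

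| Reference scan | OLE Week 48 / Week 0, groups not from Tecfidera | Same ratio, former Tecfidera |
|---|---|---|
| Previous scan | 48/24 = 2.00 | 52/24 = 2.17 to 57/24 = 2.38 |
| Study baseline | 100/52 = 1.92 to 96/48 = 2.00 | 104/52 = 2.00 to 105/48 = 2.19 |
| OLE baseline | no Week 0 count exists | no Week 0 count exists |

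**Visit windows, previous-scan reading.** With ±3 days at Weeks 24 and 48 and ±7 days at OLE Week 48, the ratio 2.00 ranges from 328/174 = 1.89 to 342/162 = 2.11 days. For former Tecfidera participants, with 28 to 70 days from the Week 48 visit to OLE Day 1 (56 + 7 window + 7 scheduling at most), it ranges from 356/174 = 2.05 to 412/162 = 2.54.

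**Later visits**
- Previous scan: from OLE Week 96 every on-schedule gap is 48 weeks, so a constant rate prints as a flat line.
- OLE baseline: counts accumulate. Without a washout, OLE Week 96 prints at 96/48 = 2 times and OLE Week 336 at 336/48 = 7 times the OLE Week 48 value.
- Study baseline: counts also keep rising.

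**EOT, previous-scan reading.** Protocol 7.3.1 asks that gadolinium exposures be at least about 4 weeks apart, and the next annual scan is due at 48 weeks. An EOT count therefore covers roughly 4 to 48 weeks, or 4/48 = 0.08 to 1.0 of an annual count, and more if a scan was missed.

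**Effect of scaling.** Take r = 1 lesion per year as an illustration. Raw means on the previous-scan reading would be 24/52.18 = 0.46 at OLE Week 0, 48/52.18 = 0.92 at OLE Week 48, 1.00 to 1.09 for former Tecfidera (52 to 57 weeks), and 4/52.18 = 0.08 for an EOT scan 4 weeks after the last. Dividing each by its interval in years returns 1.0 in every case.

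**The case against.** The strongest reply is that the size and even the direction of the artefact depend on facts the documents leave open. Protocol 7.3.1 sends further MRI detail to an Imaging Manual, and SAP 11.6 makes OLE baseline the default for OLE tables. On an OLE-baseline reading, nothing doubles at OLE Week 48. Totalling main-study T2 counts over successive scans (Protocol 8.3.2) favours a previous-scan reading, but only indirectly. This stands: a reader might infer that a doubling will certainly be printed, and the documents do not support that.

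Three further points also stand.
- SAP 16.1 does not say outright that OLE Week 0 is plotted. The Appendix 3 window and the absence of a start restriction make it likely, but the OLE EDSS plot in SAP 16.4 starts at OLE Week 48.
- A reader might infer that an EOT point distorts the curve. SAP 16.1 mentions EOT only for the table, whereas SAP 16.4 names EOT explicitly for its plot.
- A reader might infer that the whole curve reflects scan spacing. On a previous-scan reading, on-schedule gaps are equal across the four groups not from Tecfidera at every visit, and equal for all groups from OLE Week 96.

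On importance, SAP 16 states that efficacy analyses are descriptive without testing. New/enlarging T2 is not among the visible OLE endpoints in Protocol 8.3.4, although text there is redacted. A plain count by time point follows the protocol's own wording for Week 48.

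None of this rescues the raw count. Under each candidate reference scan, some part of the table or plot varies with elapsed time alone.

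**Conclusion.** The point holds in conditional form. SAP 16.1 summarises and plots unscaled counts whose time base differs between visits, and for former Tecfidera participants also between groups.

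The size depends on the reference scan. For a constant rate, the OLE Week 48 to Week 0 ratio is about 2.0 (former Tecfidera 2.2 to 2.4) against the previous scan, and about 1.9 to 2.0 (2.0 to 2.2) against study baseline. Both require Week 0 to be shown. Against OLE baseline there is no such step, but a steady rise. The tabulated EOT value, read against the previous scan, covers roughly 4 to 48 weeks unless scans were missed.

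These figures assume a constant lesion rate and scans on schedule. They do not show that the trial's results are biased in a known direction, and no estimate under test, p-value or error rate is involved. The change is worth making because the output bears on long-term efficacy and would otherwise mix scan interval with disease activity.

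**What to change.** In SAP 16.1:
- Name the reference scan for new/enlarging T2 lesions.
- By visit and at EOT, report and plot a rate: total lesions divided by total years between the reference scan and the current scan. Use the previous scan where visit-specific rates are wanted, because dividing a cumulative count by time since baseline gives a running average.
- Show the median scan interval at each visit.
- Footnote that the former-Tecfidera interval at OLE Week 48 includes the washout.
- Leave Gd+ T1 counts as raw counts.

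The cost is SAP wording, one variable derived from scan dates and a little extra programming. No new scans are needed.

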16.2 Relapses

Annualized Relapse Rates (ARR)

Descriptive statistics on relapses during the OLE period will be provided by treatment group and overall on the mITT-OLE analysis set. In particular, at the treatment-group-level, number of qualified relapses, total number of relapses (qualified or not), follow-up on treatment (in participant-years), and unadjusted ARR based on protocol-defined qualified relapses (number of qualified relapses divided by follow-up on treatment) and confidence intervals will be reported. In addition, descriptive statistics of participant-level ARR (number of qualified relapses experienced

by a participant, divided by the follow-up experienced by a participant) will be summarized for each treatment group, in terms of mean, SD, median, Q1, Q3, min, and max.

Subjects discontinuing early are analyzed according to number of years of follow-up on treatment and number of qualified relapses observed at the time of discontinuation, including data (both follow-up time and number of relapse events) from the 4-week Safety Follow-up period.

The summary will be presented for the overall OLE period (OLE Baseline – last OLE visit), for each 48-week period during the OLE, between OLE Baseline and Dose Switch during OLE, and between Dose Switch during OLE to the last OLE visit.

A listing will be provided for relapse data, by participant for the DBP and OLE treatment period combined.

16.3 Time to First Qualified Relapse and estimates

Time to first qualified relapse will be represented by a Kaplan-Meier (KM) plot on the mITT for the DBP + OLE period with orientation "increasing left to right", and with labels "Time from randomization (Weeks)" vs "Cumulative probability of qualified relapse". 1 curve will be provided for each of the 5 treatment groups. The cumulative probability of an event is estimated with PLOTS=SURVIVAL(FAILURE) option of PROC LIFETEST.

The horizontal axis should extend as far as needed to include follow-up from all participants, regardless of whether the time to an event is observed or censored.

A qualified relapse event will be counted even if it occurs after the participant has discontinued treatment.

Participants who have qualified relapse during DBP + OLE period, will have the time to first qualified relapse (weeks) calculated as "([date of first qualified relapse] – [date of first dose] + 1)/7".

Participants who do not have qualified relapse, or are lost to follow up, will be censored at the date of the last relapse assessment for this analysis. The censoring time (weeks) will be calculated as "([date of censoring] – [date of first dose] + 1)/7".

KM estimates (product-limit estimates) of the cumulative probability of experiencing qualified relapse over time will be presented in a table by treatment group, together with a summary of percentiles (5th, 10th, 15th, 20th, 25th, 30th, 35th, 40th, median) and corresponding 2-sided 95% CIs, as well as number of participants at risk, number of participants with an event, number of censored participants.

Number and percentage of subjects with qualified relapse-free status will be provided by treatment group and overall.

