8.3.4 Endpoints for Open-label Extension Period

The endpoints for the OLE Period are as follows:

- Efficacy and CCI endpoints at Week 48, 96, 144, 192, 240, 288, 336, and 384.
 - o Number of gadolinium-enhancing T1 lesions;
 - o ARR, based on protocol-defined qualified relapses;
 - Qualified relapse-free status;
 - o Change from baseline in disability score based on EDSS score;

• Safety as assessed by the nature, severity, and occurrence of AEs; vital signs; ECGs; absolute concentrations and change from Baseline in Ig levels; CCI; and clinical laboratory safety parameters.

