The purpose of this Integrated Analysis Plan (IAP) is to document technical and detailed specifications for the Final Analysis (FA) of data collected for protocol MS200527-0086 considering the early termination of the study; the primary endpoints of the phase 3 MS200527_0080 and MS200527_0082 studies were not met). The IAP is based upon Section 8 (Statistics) of the trial protocol dated 06 July 2023 (Version 8.0) and is prepared in compliance with International Conference on Harmonization E9.

This FA data report will include summaries of participant disposition, demographics, baseline characteristics, medical history, previous and concomitant medications, treatment exposure, efficacy evaluations, adverse events (AEs), deaths, selected laboratory parameters, vital signs, ECGs, and other endpoints related to safety monitoring up to the end of the study.

6 Objectives/Endpoints of the Final Analysis

The objective of the OLE Period of this study is to evaluate the long-term safety, efficacy, and HRQoL of M2951 for an additional 8 years, at an initial dose of 75 mg once daily which was eventually switched to 75 mg twice daily.

Endpoints for OLE Period:

- Efficacy and CCI endpoints at Week 48, 96, 144, 192, 240, 288, 336 and 384.
 - Number of gadolinium-enhancing T1 lesions;
 - ARR, based on protocol-defined qualified relapses;
 - Qualified relapse-free status;
 - Change from baseline in disability score based on EDSS score;

Safety as assessed by the nature, severity, and occurrence of AEs; vital signs; ECGs; absolute concentrations and change from Baseline in Ig levels;
 ; and clinical laboratory safety parameters.

For the Final Analysis, selected safety and efficacy endpoints based on data from OLE Day 1 to the end of the study will be evaluated.

For more details on the main study objectives please review section 4 Trial Objectives of the protocol.

7 Sample Size/Randomization

Sample size and randomization is described in the IAP for the primary analysis/blinded extension analysis performed after completion of the Double-Blind Period (DBP) of the study (Week 48/Week 52).

8 Overview of Planned Analyses

The protocol describes a total of 5 analyses that should be performed for this study. 4 of them have already been conducted according to the protocol. These are:

- Primary Analysis (when 100% of participants enrolled reached Week 24 of treatment, or prematurely discontinued from treatment)

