- Blinded Extension Analysis (when 100% of participants enrolled either reached Week 52 (4-week Safety Follow-up Visit) and completed the study, enrolled in the OLE, or prematurely discontinued from study)
- Safety OLE W60 Interim Analysis (when 100% of participants enrolled in the OLE reached OLE Week 60 or discontinued prematurely from the OLE prior to OLE Week 60)
- OLE W240 Interim Analysis (timed to occur shortly before the primary analysis of the Phase 3 studies in RMS, to support the results of Phase 3 studies)

The last analysis is:

• Final Analysis (triggered when 100% of participants enrolled in the OLE will complete the OLE or will discontinue prematurely from the OLE)

This IAP covers the Final Analysis. Statistical analyses will be performed using cleaned electronic Case Report Form (eCRF) data, lab and MRI data collected up until end of study. All endpoints for the OLE period will be evaluated.

9 Changes to the Planned Analyses in the Clinical Trial Protocol

There are no changes to the planned analyses in the Clinical Trial Protocol (CTP) for the Final Analysis.

10 Protocol Deviations and Analysis Sets

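### Relapse-free status during the open-label extension gets one crude percentage, with no OLE week and no rule for leavers, and no Kaplan-Meier analysis starts at OLE entry

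*SAP*

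**What the plan says.** Protocol 8.3.4 lists qualified relapse-free status among the OLE efficacy "endpoints at Week 48, 96, 144, 192, 240, 288, 336, and 384", and SAP section 6 repeats the list. SAP section 8 adds "All endpoints for the OLE period will be evaluated". Protocol 8.5.4.3 leaves the details of the OLE efficacy summaries to the analysis plan, and Protocol 8.5.1 leaves the handling of missing data to it as well.

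SAP 16.3 handles the endpoint in one sentence: "Number and percentage of subjects with qualified relapse-free status will be provided by treatment group and overall". The rest of that section is a time-to-event analysis: "Time to first qualified relapse will be represented by a Kaplan-Meier (KM) plot on the mITT for the DBP + OLE period". By its formula, time runs from the date of first dose, although the axis label says randomization. Participants without a qualified relapse "will be censored at the date of the last relapse assessment for this analysis".

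The general rules are in SAP 11.5 and 11.9. Proportions, including by-visit ones, use the number in the analysis set of interest unless otherwise specified, and missing data are not replaced. SAP 16.2 plans an annualized relapse rate (ARR) on mITT-OLE for the whole OLE, for each 48-week period, and before and after the dose switch. The SAP is written "considering the early termination of the study".

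**The concern.** OLE follow-up is unequal: participants entered and left at different times, and the study stopped early. A crude percentage free of relapse then mixes two things, the relapse risk and the length of observation. Which way it is distorted depends on a rule that the SAP does not state.

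The KM curve in 16.3 does adjust for follow-up, but it answers another question. It counts double-blind relapses as events, so a participant who relapsed in the main study can never be relapse-free on this curve, however the OLE went. It also includes mITT participants who never entered the OLE. For former Tecfidera participants its weeks do not line up with OLE weeks, because a washout of 4 to 8 weeks lies between the periods.

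The neighbouring OLE endpoints are better defined. Lesion counts (16.1), ARR (16.2) and the OLE-only EDSS summary (16.4) each name mITT-OLE, state their visits or periods, and say where early discontinuers appear. At stake is a headline descriptive figure from a long extension, whose value would be settled by a programming choice made after the data exist.

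**Working it through.** **What the documents give.** They state no expected OLE relapse-free proportion and no OLE dropout rate, so there is no figure of the plan to reproduce for this endpoint. The planned OLE size does reproduce: 250 × 0.80 = 200 (Protocol 8.1), or 200 / 5 = 40 per initial group. The only dropout figure is 12% per year, a main-study planning value (Protocol 5.1 and 8.1).

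**A result that needs no model.** With the analysis set as denominator, split the set at any OLE week into F (still followed, relapse-free), R (relapsed) and Q (left earlier without a relapse), so that F + R + Q = 1.

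- Leavers counted as free: A = F + Q.
- Leavers counted as not free: B = F. Protocol 8.5.3 uses this rule for Week 24 and does not extend it to the OLE.
- A − B = Q, the proportion that left without a relapse.

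**Illustration (assumed rates).** Constant hazards, leaving unrelated to relapse, true relapse-free proportion S at time T:

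- T = 240 × 7 / 365.25 = 4.600 years
- relapse hazard L = −ln(0.60) / 4.600 = 0.1111 per year
- leaving hazard d = −ln(1 − 0.12) = 0.1278 per year
- h = L + d = 0.2389, and hT = 1.0988
- F = exp(−1.0988) = 0.333
- R = (L/h)(1 − F) = 0.4649 × 0.6667 = 0.310
- Q = (d/h)(1 − F) = 0.5351 × 0.6667 = 0.357
- A = 0.333 + 0.357 = 69.0%, and B = 33.3%

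A KM analysis from OLE start estimates S = 60% under these assumptions. Other inputs, same formulas:

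| OLE week | True S | Leaving per year | A | B | A − B (points, unrounded inputs) |
|---|---|---|---|---|---|
| 240 | 60% | 12% | 69.0% | 33.3% | 35.7 |
| 240 | 60% | 5% | 64.0% | 47.4% | 16.6 |
| 48 | 90% | 12% | 90.6% | 80.0% | 10.5 |

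With S from 50% to 90% at Week 240 and 5% or 12% leaving, A lies 1.1 to 10.9 points above the KM value and B 10.5 to 40.0 points below. At Week 48 with S of 90% or 95%, A is 0.1 to 0.6 points above and B 4.1 to 10.5 below.

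**Effect of the time origin (also assumed rates).** Take an OLE relapse rate of 0.10 per year and 52.18 weeks per year. Relapse-free from OLE start to Week 240 is exp(−0.10 × 240/52.18) = 63.1%. From first study dose, the same calendar point is study Week 288 for a participant without a washout. The value is then multiplied by exp(−r × 48/52.18), where r is the double-blind relapse rate. It becomes 57.6%, 52.5% or 43.7% for r = 0.1, 0.2 or 0.4 per year. The existing curve therefore cannot be read as OLE relapse-free status.

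**The case against.** The strongest reply is that the sentence has a natural meaning. It follows a table of participants with an event and participants censored, in a section that names mITT and the combined period. On that reading the percentage is the complement of those with an event, and leavers count as free. The defaults in SAP 11.2 and 11.3 yield where a section specifies otherwise. This is a reasonable reading, but it does not rescue the endpoint: the percentage would then count double-blind relapses and name no OLE week, so no OLE relapse-free figure would be produced. If the OLE default in 11.3 applies instead, the leaver rule is still missing.

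Other replies stand in part. All efficacy output is descriptive (SAP 16). The ARR in 16.2 adjusts OLE relapse counts for follow-up, although it does not give the proportion relapse-free to a given week. Discontinuations are already tabulated by reason in SAP 12.1. The Protocol asks only that OLE efficacy be summarized, so it does not itself require a KM analysis. The by-week figures above apply to the endpoint as listed, not to the single percentage that 16.3 describes.

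A reader might also infer more than the documents support:

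- **That leavers might be dropped from the denominator, or only those still in the trial counted.** SAP 11.5 sets the percentage denominator as the analysis set even for by-visit work, so neither applies unless stated. Its remark about the population still in the trial concerns the totals of missing and non-missing observations.
- **That early termination forces the figure to 0% at the last listed weeks if leavers count as not free.** This needs assumed start and stop dates. It also treats participants stopped by the sponsor as leavers, while SAP 12.1 classes them as having completed OLE treatment. That is a disposition definition, but it makes such figures unsafe.

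**Conclusion.** The concern holds as a gap in the analysis of one listed OLE endpoint. No planned output gives follow-up-adjusted relapse-free status from OLE start. The one percentage that is planned can fall on either side of the KM value, according to an unstated rule. The spread between the two classifications equals the proportion that left without a relapse, whatever the relapse rate. It is 35.7 points at Week 240 in the example, but that size rests on an assumed 60% relapse-free, a main-study planning dropout rate, constant hazards and leaving unrelated to relapse. If leavers count as free, the departure from KM is under 1 point at Week 48 on the rates tried, so the problem is mainly one of the later weeks.

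The point does not extend to type I error, power or any treatment comparison, and it does not mean that OLE relapse activity is reported without regard to follow-up. The change should be made, because a better analysis is available from data already collected.

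**What to change.** Add to SAP 16.3 a KM analysis of time to first qualified relapse from first OLE dose on mITT-OLE, by initial treatment group and overall, censored at the last relapse assessment. Report the relapse-free probability, 95% CI and number at risk at each listed OLE week that is reached. Note beside it that KM assumes non-informative censoring, and refer to the discontinuation reasons in SAP 12.1, since Protocol 5.6.1 lists lack of efficacy as a ground for withdrawal.

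If the n (%) is kept, state its set, period and leaver rule, and label it as not adjusted for follow-up. Keep the existing combined-period KM.

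The cost is one more table, with imprecise late estimates by group. On the Week 240 example, the expected number at risk is N × F = 40 × 0.333 = about 13 per group. The Greenwood standard error, S × √[(L/h)(exp(hT) − 1)/N] = 0.60 × √(0.4649 × 2.0006/40), is about 9 points. Pooled over 200, about 67 are at risk and the standard error is about 4 points. The censoring assumption cannot be checked from the table itself.
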